## Statistical Analysis Plan

The UAB Pediatric CBD Program enrolled 89 treatment resistant epileptic children ages 1-19 years old. All study participants received Epidiolex drug (Cannabidiol; CBD) as an add-on to their previously stable anticonvulsive treatment after baseline assessment. Participants received a starting dose of CBD at 5 mg/kg/day in twice daily dosing and titrated by 5 mg/kg/2 weeks up to 25 mg/kg/day, with a maximum dose of 50 mg/kg/day. Seizure frequency, severity, and adverse events together, with other clinical participant measures, were assessed at baseline and bi-weekly for the duration of the study.

The first 12-months (1-year) of follow-up data were analyzed as follows:

1. The primary outcome measures included:

- a. Severe adverse events (increase in seizure frequency by more than 100% leading to emergency room visit or hospitalization),
- b. Change in resting blood pressure or heart rate by 25% if considered significant by managing neurologist,
- c. Any change in, CBC, CMP, Liver function tests (LFTs), Urinary Analysis or Antiepileptic drug (AED) levels considered by managing neurologists as clinically significant. Clinically significant will be determined by using the Common Toxicity Criteria for Adverse Events (CTCAE) Version 4.03. Adverse events (AE) categorized as a grade 3 or above will be considered clinically significant. Adverse Events graded 4 or above will be considered severe adverse events (SAE).

The analysis plan was focused on safety. The information on safety was tabulated as the percent of participants with each safety outcome AE and SAE, or others reported as meaningful as well as the number of occurrences of each AE and SAE. This enabled an event rate calculation per exposure time as well as the average number of occurrences per participant with an AE or SAE.

2. The secondary analysis assessed the frequency and severity of seizure outcome measures to include:

- a. Mean (SD) and median (IQR) decrease in seizure frequency as measured in total number of seizures per month.
- b. Mean (SD) and median (IQR) decrease in seizure severity as measured by the Chalfont Seizure Severity Scale (Duncan & Sander, 1991, JNNP).

The analysis plan for frequency and severity of seizures (secondary outcome measures) assessed the pattern of change over time relative to baseline. The non-parametric Friedman's test was used since seizure frequency and severity outcome measures were not normally distributed. Wilcoxon's signed rank test with Bonferroni's multiple comparison correction was utilized as a post-hoc analysis for pairwise comparisons between baseline and each post-baseline time point.

Further parametric analysis used the generalized least squares statistical techniques for modeling longitudinal data, an extension of mixed effects models that accommodates heteroscedacity and correlation within group errors (Pinheiro and Bates, 2000), after normality of outcome measures were achieved through log-transformation methods. The longitudinal analysis included each month following baseline up to the 12-month endpoint, with a log transformation of seizure measures regressed on time (months), gender, and several identified baseline clinical variables including number of AEDs, number of AEDs tried, and history of epileptic surgery. A cubic spline with 4 knots (carefully chosen with AIC and BIC) was put on time to capture the non-linear trend in seizure outcome measures. AIC and BIC also aided in the choice of the specified correlation structure for this analysis.

Effectiveness of CBD exposure on the population of interest was established with contrast estimates of percentage reduction in seizure outcome measures at each post-baseline time point relative to baseline from model.

Both parametric and non-parametric methods were repeated using last observation carried forward (LOCF) principle on the data instead of complete cases of the data. An alpha level of 5% was used to achieve statistical significance.

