The interactions between CBD and other drugs that are metabolized in a similar manner are not well understood. There may be an increased risk of toxicity and or side effects such as sedation when CBD is administered with other anti-epileptic drugs. If there is a suspicion that a change in the patient's clinical status may be attributed to such concomitant medication, careful monitoring of plasma levels of the medication and/or its metabolites should be followed. Periodic blood levels of anti-epileptic drugs may need to

be measured during the course of this study. If you experienced symptoms of toxicity such as drowsiness and feel that you need a blood test to determine if other anti-epileptic blood levels have been increased by CBD, tell the doctor or nurse involved in this study. Also, you should tell other doctors or nurses who care for you that you are on this investigational drug.

It is important to know that long-term use of CBD has not been studied in any patients with seizures/epilepsy. The risks to younger children, when considering growth and development, from long-term CBD exposure are unknown at this time. Also, there is no specific information available about use of CBD in patients with kidney or liver problems/failure.

The use of CBD may have no impact on, a reduction of, or a worsening of seizures/epilepsy.

Driving and/or use of machinery

The study medication may produce side effects such as dizziness, or feeling drunk, sleepy or abnormal. This may affect the ability to do skilled tasks. Subjects are advised not to drive, use machinery or take part in any dangerous activity until it is known that the study medication is not affecting their ability to do these tasks.

Alcohol

Alcohol may interact with the study medicine and produce a much more powerful effect than usual, which can easily cause accidents in the home or elsewhere. Subjects are strongly advised either to avoid alcohol for the duration of the study or to consume it in moderation. Moderate consumption of alcohol is defined by the Royal College of Physicians as 15 to 21 units per week for men (7-10 pints of beer or standard 175 ml glasses of wine in a week) and 11 to 14 units per week for women (5-7 standard 175 ml glasses of wine in a week).

Travel

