Adverse Events (AEs) for this study are defined as the appearance of (or worsening of any pre-existing) undesirable sign(s), symptom(s), or medical condition (s) that may occur after the patient's signed the informed consent for the study. Abnormal laboratory values or test results occurring after the informed consent is signed constitutes adverse events only if they induce clinical signs or symptoms, are clinically significant, require therapy, or changes in study medication(s).

AEs that begin or worsen after the informed consent should be recorded in the Adverse Event CRF and will be entered in the UAB CBD data coordinating center database. Conditions that are already present at the time of informed consent will be documented as part of the patient's medical history. Subjects and their families will be provided with contact information in order to notify study personnel of any adverse events, with availability at all times. Upon notification of an AE, a determination will be made by study personnel with regard to whether the AE is study related. This determination will be made within 24 hours of receipt of documentation of the AE. If the AE has involved participation of any other medical personnel or facilities, documentation of that activity will be obtained by study personnel for review. The AE will be monitored until it has resolved by the study investigator. AEs will be assessed to determine the following parameters: severity, duration, relationship to the CBD administration, action taken or treatment instituted, and whether the AE meets the criteria for a serious AE. Adverse Events will be assessed according to the Common Terminology Criteria for Adverse Events (CTCAE).

All clinically significant abnormalities noted upon physical examination, or other diagnostic test results should be reported as an AE, except for baseline measurements that may be considered part of the medical history. In addition, all clinically significant AEs that continue at Study Termination should be followed up by the investigator and evaluated with additional tests if necessary, until the underlying cause is diagnosed or resolved, or is determined to have resolved with sequelae. All AEs will be evaluated for

intensity and causal relationship with use of the study medication (or study procedures if applicable) by the investigator.

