AEs that occur following completion of study termination/early termination procedures should be recorded on the AE page of the source documents only if the investigator considers the event as clinically significant and as related to study medication or study procedures.

All adverse events that are deemed to be serious and meet the definitions provided in section below for serious adverse events will be reported as SAEs.

Serious Adverse Events :

Serious adverse event is defined as “ANY TREATMENT EMERGENT SAE THAT OCCURS AFTER THE SIGNING OF THE INFORMED CONSENT FORM through 30 DAYS after administration of the last dose of study medication. Any AE that results in any of the following outcomes will be considered an SAE. The following outcomes are defined according to Code of Federal Regulations (CFR) Title 21 part 312.32.

- Death
- Life-threatening situation (subject was at risk of death at the time of the event. This does not refer to an event that might have caused death if it was of greater intensity.)
- Inpatient hospitalization or prolongation of existing hospitalization
- Persistent or significant disability or incapacity
- Congenital anomaly or birth defect
- Important medical events that may not result in death, be life-threatening, or require hospitalization but may jeopardize the subject and may require medical or surgical intervention to prevent one of the above outcomes (based upon appropriate medical judgment), e.g., allergic bronchospasm requiring intensive treatment in an emergency room or at home, blood dyscrasias or convulsions that do not result in inpatient hospitalization, or the development of drug dependency or drug abuse.

The term “severe” is often used to describe the intensity (severity) of a specific event (as in mild, moderate, or severe pain); the event itself, however, may be of relatively minor medical significance (such as severe headache). By contrast, the term “serious” is used to describe an event based on an event outcome or actions usually associated with events that pose a threat to a patient’s life or functioning. Seriousness (not severity) serves as a guide for defining regulatory reporting obligations.

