It is important to know that long-term use of CBD has not been studied in any patients with seizures/epilepsy. The risks to younger children, when considering growth and development, from long-term CBD exposure are unknown at this time. Also, there is no specific information available about use of CBD in patients with kidney or liver problems/failure. The study includes frequent visits and safety lab assessments to monitor renal and liver function while participants are taking CBD.

GW Pharma will not participate in the analysis of our study data. GW will collect certain data from our study to perform their own analysis.

Members of the DSMB will include:

[name], PhD (Chair of the DSMB)
[name]
[name].
[name].
[name], Statistician

The DSMB members will not perform any protocol driven activities or procedures.

Data Analysis

The Adult and Pediatric protocols will enroll a combined total of 100 subjects. The data analysis will be split into groups based on age ranges. The groups will be divided as follows: Toddler/Early Childhood (1-5 years of age), Middle Childhood (6-11 years of age), and Early Adolescence (12-18 years of age), and Adults (19+ years of age).

After the 100 subjects have been enrolled and followed for 1 year the following data analysis will be performed:

1. The safety outcome measures will be the Primary Measure and will include:
 - a. Severe adverse events (increase in seizure frequency by more than 100% leading to emergency room visit or hospitalization),
 - b. Change in resting blood pressure or heart rate by 25% if considered significant by managing neurologist,
 - c. Any change in, CBC, CMP, Liver function tests (LFTs), Urinary Analysis or Antiepileptic drug (AED) levels considered by managing neurologists as clinically significant. Clinically significant will be determined by using the Common Toxicity Criteria for Adverse Events (CTCAE) Version 4.03. Adverse events categorized as a grade 3 or above will be considered clinically significant. Adverse Events graded 4 or above will be considered severe adverse events (SAE).

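### The diary analysis gives no count of children whose seizures worsened, and primary safety item 1a names worsening only when a more-than-doubling leads to emergency care or admission

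*SAP*

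**What the plan says.** **Primary safety outcome.** The protocol's Data Analysis section states "The safety outcome measures will be the Primary Measure and will include", and item 1a there, in the protocol's Specific Aims and in the SAP is the same: "Severe adverse events (increase in seizure frequency by more than 100% leading to emergency room visit or hospitalization". Item 1c adds a grading route: "Adverse Events graded 4 or above will be considered severe adverse events (SAE".

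**Safety tabulation.** In the SAP, "The information on safety was tabulated as the percent of participants with each safety outcome AE and SAE, or others reported as meaningful", with the number of occurrences of each.

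**Diary analysis.** SAP item 2a is "Mean (SD) and median (IQR) decrease in seizure frequency" per month, and item 2b treats severity likewise. The SAP then tests change from baseline (Friedman, Wilcoxon) and reports model contrasts as percentage reductions. The protocol's Data Analysis section also plans individual thresholds of control, but the examples it gives (10%, 25%, 50%) are all reductions.

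**Worsening as a risk.** The protocol's section on risks and side effects says: "The use of CBD may have no impact on, a reduction of, or a worsening of seizures/epilepsy".

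**The concern.** Both documents say that the analysis is focused on safety, and the protocol names worsening seizures as a possible effect. Item 1a nevertheless leaves out a child whose seizures rise by 60%, one whose seizures triple but are managed at home, and one admitted after a 90% rise. Its second condition measures use of care as well as seizures.

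The diary is collected from every child throughout and could supply the missing count. As planned, it yields group summaries in which worsened children are offset by improved ones. The protocol's control thresholds do not help: a child who misses the 10% reduction may be unchanged or worse. In an uncontrolled paediatric study, the proportion of children whose seizures became more frequent is a basic result, and the plan does not produce it.

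**Working it through.** **The plan's own figure.** The documents give no number on worsening. The nearest is the precision statement in the protocol's Data Analysis section: a two-sided 90% normal-approximation interval at n = 100. For p = 0.10, 1.645 × √(0.10 × 0.90/100) = 0.0493, which matches the stated 0.049. At the 89 children enrolled (SAP) it becomes 0.0523.

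**How many can worsen unseen in the median and IQR?** With 89 ordered changes and the usual interpolation, the upper quartile is at position 1 + 0.75 × 88 = 67. If 67 children improve and 22 worsen, the 67th value is still a decrease. With 23 worsened (25.8%) the upper quartile becomes an increase. So 22/89 = 24.7% is the maximum.

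Invented example: 67 children at −50% and 22 at +60%.
- Quartiles: −50%, −50%, −50%.
- Mean: (67 × −50 + 22 × 60)/89 = −2030/89 = −22.8%; SD about 48 points.
- Item 1a: 0 of 89, since nobody exceeds +100%.

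The mean and SD hint at a mixed response but do not give the count.

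**How much worsening could the doubling condition miss?** Assumption, not in the documents: the individual follow-up/baseline ratio is lognormal with median 0.5 and log-SD s. Then P(ratio > r) = 1 − Φ[(ln r − ln 0.5)/s].

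| s | any increase, of 89 | above 100%, of 89 | share above 100% |
|---|---|---|---|
| 0.5 | 7.4 | 0.2 | 3% |
| 0.8 | 17.2 | 3.7 | 22% |
| 1.0 | 21.7 | 7.4 | 34% |
| 1.2 | 25.1 | 11.0 | 44% |

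With median reductions from 30% to 60%, the share runs from about 2% to 50%. The care condition reduces it further.

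**How much apparent worsening is chance?** Inputs: 4 seizures a month, the minimum in the protocol's inclusion criteria; a month taken as 28 days; Poisson counts; no true change. An 84-day window then expects 12 seizures.

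*Baseline known, one fixed window:*
- Any increase: P(X ≥ 13 | 12) = 42%.
- At least 50%: P(X ≥ 18 | 12) = 6.3%.
- Above 100%: P(X ≥ 25 | 12) = 0.07%.

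*Baseline B an unselected three-month count, also with mean 12:* the protocol's enrollment procedures require a calendar of at least three months. Summing Poisson(b; 12) × P(X ≥ 1.5b | 12) over b gives 17.9% for at least 50%. The same sum gives 4.7% for above 100% and 46% for any increase.

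*Baseline known, any rolling 84-day window in 364 days:* simulation of 100,000 children gives 53% for at least 50% and 1.6% for above 100%.

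A single month is noisier still: P(X ≥ 9 | 4) = 2.1% for above 100%, and 1 − (1 − 0.0214)^12 = 23% for at least one such month in twelve.

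**The case against.** A reader might infer that worsening reaches the safety results only through item 1a. The documents do not support that.
- The protocol's Adverse Events section counts as an AE "the appearance of (or worsening of any pre-existing) undesirable sign(s), symptom(s), or medical condition (s", and says that events beginning or worsening after consent should go on the AE form.
- Its Serious Adverse Events section includes among its examples "blood dyscrasias or convulsions that do not result in inpatient hospitalization".
- The visit procedures give the doubling criterion as an example, not as a definition.
- Grade 4 or above is another route, although that sentence follows the laboratory items.
- The SAP tabulates AEs and SAEs generally, and staff review diaries and AEs at scheduled contacts after dosing starts.

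All of this stands. What remains is that these routes rest on investigator reporting, with no stated frequency threshold for calling a rise in seizures an AE. In children with at least 4 seizures a month at entry, a gradual rise may be judged background disease.

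A reader might also infer that the diary analysis ignores worsening. It does not. A mean, SD, median and IQR of decrease are signed, and the tests and the model use all values. Worsening is in the data but is not shown as a count.

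Finally, a table of diary increases could itself mislead. If a rise in any rolling window counted, about half of unchanged children at the entry minimum would be flagged at the 50% level. That objection is right about rolling windows and is why the window must be fixed.

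**Conclusion.** The point holds as a gap in display. Item 1a names only more-than-doubling that leads to emergency care or admission, and no planned diary summary counts children who worsened. Up to 22 of 89 could have worsened with the median and both quartiles still showing a decrease. This is the largest number compatible with those summaries, not an estimate, and it assumes that all 89 contribute a value.

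A reader might go further and conclude that worsened children are under-counted. The documents show only that they may be, because the yield of AE reporting and the spread of individual change are unknown. Complete-case analysis could hide more if worsened children leave early. The SAP repeats its analyses with last observation carried forward, but for the same group-level summaries.

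The chance rates rest on Poisson counts at the entry minimum. Greater month-to-month variability would raise them, and higher baseline rates would lower those for the 50% and 100% rows. Selection on a high baseline count would also lower them; the protocol itself notes that the historical baseline may overstate severity.

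**What to change.** Keep item 1a. Add one descriptive table beside the safety results, derived from the diary and regardless of emergency care. It should give n/89 (%) with a confidence interval for children with:
- any increase over the baseline calendar rate;
- an increase of at least 50%;
- an increase above 100%.

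Use one fixed window written into the SAP, for example the last 84 days of the 12 months, or the last 84 days on study for children who leave early. Do not use any rolling window. State how dropouts are counted, including those with less than 84 days of diary.

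Print the chance rates beside the rows. At 4 seizures a month, the 50% row is about 6% with a known baseline and about 18% with a three-month baseline count. The any-increase row is 42% to 46% and is useful only as description. A two-sided 90% interval would match the protocol's precision statement; at 22/89 its half-width is 1.645 × √(0.247 × 0.753/89) = 0.075.

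The cost is one more table from data already collected, a possibly less favourable safety picture, and some chance misclassification at low baseline rates. No visit or clinical rule changes.

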
(Bayley-III®)-Emotional Assessments will be completed by the parent or LAR of the participant, instead of the NIH Emotional Measures assessments.

^e Laboratory Assessments collected at Study Visit 1 will include a CMP and CBC. The study doctor may order additional laboratory testing (blood and/or urine tests) at follow up study visits to assess for side effects and toxicity. The laboratory assessments would include: CMP, CBC, Liver Functional Tests (LFTs), Urinary Analysis and any anti-epileptic drug (AED) levels). Subjects approved for the UAB CBD Open Access Program must have laboratory studies within 3 months of the committee review which include: CBC, Complete Metabolic Panel, Urine Analysis and anti-epileptic drug levels. If the subject enrolls in the program and completes the screening visit within 3 months of the required baseline laboratory studies, they are not repeated at Study Visit #1. If the subjects enrolls outside the three month window, the laboratory studies are repeated (CBC, CMP, anti-epileptic medication levels) at Visit #1. During the initial 3 months of the titration of CBD up to 25 mg/kg/day (study visit every 2 weeks), repeat laboratory studies will be done at 4-week intervals until the 6-month visit and then every 3 months (9-month and 12-month visit) and then at 6-month intervals for the duration of the study. At each visit, complete vital signs are taken and review of potential adverse events and menstrual history will be done. If there is any concern of the anti-epileptic medication interaction with CBD, additional AED levels are drawn at the study visit. Particular attention is given if the subject is currently taking valproic acid and clobazam because of potential drug interactions. A urine analysis is completed at Study Visit #1 and will be completed as needed throughout the protocol to monitor for toxicity or potential side effects. A urine analysis schedule will be added at 3-month intervals during the first year of the study and every 6 months for years 2 and 3. An ECG is obtained as part of the screening process, but will be repeated at 6 months, 12 months and then yearly while participants are enrolled in the study. The early discontinuation visit will include a CBC, CMP, UA and an ECG.

^f Patients have the option of participating in an fMRI Substudy.

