Subsequent Visits: Study Visit 8/Day 112/Wk 16/Month 4 (+/- 7 days), Study Visit 9/Day 140/Wk 20/Month 5 (+/- 7 days), Study Visit 11/Day 252/Wk 36/ Month 9 (+/- 7 days), Study Visit 12/Day 336/Wk 48/ Month 12, Study Visit 13/Day 420/Wk 72/ Month 18, Study Visit 15/Day 588/Wk 120/ Month 30, Study Visit 16/Day 672/Wk 144/Month 36, Study Visit 17/Day 756/Wk 168/ Month 42:

Procedures for these visits will include:

- Adverse Event and Serious Adverse Event Monitoring (e.g., increase in seizure frequency by more than 100% leading to emergency room visit or hospitalization)
- Seizure Diary Data reviewed and collected by study staff
- Menstrual History collected by study staff
- Chalfont Seizure Severity Scale
- Vital signs: Age, Weight, Height, Heart Rate, and Blood Pressure, Temperature
- Urine Pregnancy Test (only for women of child bearing potential)

- CBC and CMP (collected at SV8, SV9, SV12, SV16 only); Study doctor may order additional laboratory testing (blood and/or urine tests) and/or more frequent testing to assess for side effects and toxicity. The laboratory assessments would include: Liver Functional Tests (LFTs), Urinary Analysis and any anti-epileptic drug (AED) levels,
- Physical and Neurological Examination
- Columbia-Suicide Severity Rating Scale (C-SSRS)
- AEP Questionnaire
- NIH Toolbox for Emotional Assessment**: Emotion Measures from the NIH Toolbox will be administered to each participant and/or their legal guardian. The Emotion Measures from the NIH Toolbox assess four major domains: Negative Affect (NA), Psychological Well-Being (PWB), Social Relationships (SR), and Stress/Self-Efficacy (SSE). ****Performed at Study Visit 12/Day336/Wk48/Month 12 only****

For participants ages 3 – 7, the following age-appropriate subtests from the NIH Toolbox Emotion Parent Proxy Battery will be administered:

- Negative Affect
 - o NIH TB NA Anger – Parent Report
 - o NIH TB NA Fear-Over Anxious Parent Report for Children
 - o NIH TB NA Fear-Separation Anxiety Parent Report FFSF
 - o NIH TB NA Sadness Parent Report FFSF for Children
- Psychological Well-Being
 - o NIH TB PWB General Life Satisfaction Parent Report SF-FF
 - o NIH TB PWB Positive Affect Parent Report CAT
- Social Relationships
 - o NIH TB SR Empathic Behaviors Parent Report CAT
 - o NIH TB SR Peer Rejection Parent Report FFSF
 - o NIH TB SR Positive Peer Interaction Parent Report FFSF
 - o NIH TB SR Social Withdrawal Parent Report FF-SF

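### Primary safety outcome 1b counts a 25% change in blood pressure or heart rate only if an unblinded neurologist judges it significant, and the SAP plans no analysis of the vital-sign values themselves

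*SAP*

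**What the plan says.** The SAP lists three primary safety outcomes. Item 1b is "Change in resting blood pressure or heart rate by 25% if considered significant by managing neurologist", and the Data Analysis section of the protocol words it identically. Item 1c, on laboratory tests, carries an explicit standard: "Clinically significant will be determined by using the Common Toxicity Criteria for Adverse Events (CTCAE) Version 4.03", with grade 3 or above counted. Item 1b has no such sentence.

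For the analysis, "The information on safety was tabulated as the percent of participants with each safety outcome AE and SAE", together with the number of occurrences, an event rate per exposure time and the average number of occurrences per affected participant. The protocol adds Kaplan-Meier curves for common events. Neither document plans a summary of heart rate or blood pressure as measured values.

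The values exist. The laboratory footnote to the protocol's schedule of events says "At each visit, complete vital signs are taken". The SAP covers one year ("The first 12-months (1-year) of follow-up data were analyzed as follows") in a programme that "enrolled 89 treatment resistant epileptic children ages 1-19 years old". All of them received cannabidiol (CBD), and the protocol states that the study is not randomized.

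**The concern.** An event under 1b has two parts: a 25% change, and a neurologist's opinion that it matters. The opinion comes from someone who knows the child is on CBD and has no written standard to apply. Two neurologists could count the same readings differently, and the report would not show it.

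The numeric part has problems of its own. Repeated comparison with a baseline reading gives many chances to cross 25% through ordinary variation. A moderate shift shared by most children may leave few readings past the threshold. With no control group there is no reference rate for the resulting percentage. At stake is whether a primary safety outcome can say anything about CBD's effect on heart rate or blood pressure. The seizure outcomes, which are secondary, get means, medians, rank tests and a longitudinal model. Outcome 1b, also based on repeated numeric readings, gets only a filtered count.

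**Working it through.** **The plan's own figure.** The documents give no precision for 1b. The nearest figure is the half-width of a 90% interval for a proportion at n = 100 in the protocol's Data Analysis section: 1.645 × √(p(1−p)/100) = 0.049, 0.066, 0.075, 0.081 and 0.082 for p = 0.10 to 0.50. All five reproduce. At n = 89 and p = 0.50 the half-width is 0.087. These describe sampling error in the count, not what the count means.

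**Number of looks.** The protocol schedules in-person visits SV2 to SV12 on days 14, 28, 42, 56, 70, 84, 112, 140, 168, 252 and 336, the last being "Study Visit 12/Day 336/Wk 48/ Month 12". That is 11 post-baseline visits. The SAP says measures "were assessed at baseline and bi-weekly for the duration of the study", which does not match this schedule and would mean more looks. I use 11.

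**Chance of crossing 25% with no drug effect.** Within-child visit-to-visit CVs are not in the documents, so they are assumed and varied. Each simulated child has one baseline and 11 follow-up readings, normally distributed with the stated CV and independent. A hit is |follow-up/baseline − 1| ≥ 0.25 at any visit, in either direction.

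| Heart-rate CV | 5% | 6% | 8% | 10% | 12% | 15% |
|---|---|---|---|---|---|---|
| Children with a hit, heart rate alone | 1% | 4% | 19% | 42% | 63% | 85% |

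- Lognormal readings give nearly the same figures.
- At a single visit the heart-rate rate is about 3% at CV 8% and 8% at CV 10%, so the 11 looks drive the increase.
- Averaging two baseline readings cuts 19% to 10% (CV 8%) and 42% to 31% (CV 10%).
- For any of heart rate, systolic or diastolic pressure, taken as independent, the share is about 4% at CVs of 5%, 4% and 6%. It runs from 36% (CVs 8%, 6%, 8%) to 99% (CVs 15%, 10%, 15%).
- An assumed growth drift over the year (heart rate −3%, pressures +2%) changes the three-measure share by one percentage point or less.

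**Response to a real shift.** Suppose heart rate truly rises by 10% in every child. The heart-rate screen moves from 19% to about 47% at CV 8%, from 42% to 60% at CV 10%, and from 63% to 73% at CV 12%.

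**Effect of the judgement.** The reported count is the screen times an unknown share judged significant. Take lognormal readings with CVs of 10%, 8% and 12% for heart rate, systolic and diastolic pressure. The three-measure screen moves from 82% to 89% under the same 10% rise. If 5% of affected children are judged significant, that is 3.7 against 4.0 children of 89; if 50%, 36.5 against 39.5. The judged share changes the count roughly tenfold, while the shift changes it by under a tenth. This illustration assumes the judged share does not depend on the size of the change.

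**What the values would show.** The 95% half-width of mean change at one visit, with all 89 children measured, is 1.96 × CV × √2/√89:

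- CV 5%: 1.96 × 5 × 1.414/9.434 = 1.5%
- CV 8%: 2.4%
- CV 10%: 2.9%
- CV 15%: 4.4%

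A 10% mean change would lie well outside these limits. Children leaving the study, or responding differently from one another, would widen them.

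**The case against.** The strongest reply is that 1b detects events and was never meant to estimate a mean. A clinician's judgement is a reasonable way to discard chance excursions, so a high screen rate says nothing directly about the reported count. That is fair. A reader might infer that the count is mainly noise or mainly opinion, but no figure in the documents shows what share of 25% changes is judged significant.

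The simulated rule is also one reading of an under-specified text. Any visit, either direction and a single baseline are assumptions. Vital signs are scheduled at both the enrollment visit and SV1 unless the two are combined, so two baseline readings may exist. Participants may leave at any time, so 11 visits is a ceiling under the protocol schedule.

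There are other routes for safety signals. The protocol's Adverse Events section has clinically significant abnormalities recorded as adverse events and assessed by CTCAE, and the safety board periodically reviews all study data. These could catch marked changes. They do not define significance in 1b or add an analysis of the values to the SAP, so a moderate shift could be missing from the SAP's tables, which is narrower than being missed altogether.

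Finally, a mean change without controls is no more a drug effect than the count is. That stands, and limits what the fix can claim.

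**Conclusion.** Outcome 1b depends on an unblinded judgement with no stated criterion and leaves the measure, direction and reference reading open. The SAP plans nothing on the measured values. The count is insensitive to a systematic shift below 25% and cannot be interpreted as a drug effect. This follows from the text and does not depend on the simulation.

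The size of the chance component does depend on assumption: about 1% to 85% of children for heart rate across CVs of 5% to 15%, with one baseline reading and full attendance. Three stronger conclusions are tempting and are not supported:

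- That many or most children would cross 25% by chance. This holds only at the higher assumed CVs.
- That growth drives the crossings. The assumed drift adds a point or less.
- That the count cannot reveal a real shift. At CV 8% the heart-rate screen more than doubles under a 10% rise.

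The change is worth making because it is cheap and the outcome is primary. It does not invalidate the other safety tables.

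**What to change.** In SAP item 1b:

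1. State the baseline reading (for example SV1, or the mean of the enrollment and SV1 readings where both exist), and treat heart rate, systolic and diastolic pressure separately.
2. For each, report change from baseline with a 95% confidence interval at every scheduled visit, as percent change or against age references. Describe it as uncontrolled.
3. Report the number of children with any change of 25% or more, increases and decreases separately, and the number with such a change at two consecutive visits.
4. Show the neurologist-judged count beside these, not as a condition on them, and state the criterion used for significance.
5. Reconcile the SAP's bi-weekly assessment statement with the protocol visit schedule.

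The cost is SAP wording and a few tables from readings the protocol already collects. The downsides are that the ungated count will be at least as large as the judged one and needs a sentence of explanation, and that the mean change still has no concurrent comparison.
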